Study Design: We propose a prospective, randomized, trial of oral DHA supplementation of lactating mothers. Cincinnati Children's Hospital research staff will screen all infants admitted to the Cincinnati University Hospital NICU on a weekly basis. Eligible participants will be identified by the Principle Investigator and the research coordinator. Potential participants (mothers) will be approached regarding the possibility of study participation by study staff trained in the consent process. Eligible participants will be screened and if eligible and interested, will be consented within one week of being admitted to Cincinnati University Hospital NICU. Maternal consent will be obtained for the infant. Consent will be administered by Cincinnati Children's Hospital Medical Center staff trained in the consent process and having completed all required CITI training. Informed consent will be documented by an Informed Consent Process Note. All data and infants biological sample collection will take place during the infants stay in Cincinnati University Hospital NICU. Mother's biological samples will be collected by Cincinnati University Hospital NICU. Study staff and Hoxworth outpatient lab.

After informed consent, lactating mothers will be randomized by The Cincinnati University Hospital Investigational Pharmacy to receive DHA (DHA- Martek Biosciences, now known as DSM Nutritional Lipid- Expecta®) 200 mg, or 1000 mg/day. The randomization schedule has been devised in collaboration with the Biostatistics expert, [name], identified in these studies. We have used the Consolidated Standards of Reporting Trials (CONSORT)framework [33].

Participants who meet any exclusion criteria during the course of the study, are non-compliant or are lost to follow-up will be withdrawn. Provided that there are at least 8 mother/baby pairs with evaluable data in each group, withdrawn participants will not be replaced. Anticipated enrollment will take two years.

Inclusion criteria: Lactating mothers at Cincinnati University Hospital with infants born at <29 weeks gestation admitted to The Cincinnati University Hospital NICU

Exclusion criteria:

- Infants with the presence of congenital anomalies (trisomy 13, 18, 21, urethral, gastrointestinal and cardiac defects) that affect the standard course of care.
- mother's <18 and
- mothers with known allergy to algeal source

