Statistical Plan: All data analyses will employ intention to treat principles. In our primary analysis, ANOVA will be used to compare DHA levels at four weeks in the breast milk of mothers assigned to the different concentrations of DHA supplements. As in any prospective study, If we experience substantial loss to follow-up (e.g., > 10% of subjects), we will fit a linear mixed model [35] We will use two sample t tests to compare infant blood DHA concentrations and TNF-alpha and IL-10 levels at 8 weeks of infants randomized to DHA-supplemented milk. The comparison of DHA concentrations will be performed at a significance level of 0.05 while the comparison of TNF-alpha and IL-10 levels will be performed at a significance level of 0.025 to adjust for the two outcomes. All analyses will be performed using SAS (SAS Inc., Cary, NC). Our sample size determination to detect a two-fold difference in the DHA levels at four weeks in expressed milk of mothers assigned DHA treatments, we will need data on a total of 16 mothers at week 4 (8 per group). This sample size calculation was based on 90% power, a two-sided significance level of 0.025, and a coefficient of variation (CV) of 30%; the CV is based on a previous study [36]. Assuming a conservative 20% loss to follow-up before week 4, we will enroll enough mother-infant pairs to achieve our desired sample size of 16 at 4 weeks. It is expected that evaluable data at week 4 from at least sixteen of the mother/baby pairs (8 pairs per group) will be obtained. The University Hospital Investigational Pharmacy will randomize participants per the Consolidated Standards of Reporting Trials (CONSORT) framework. Secondary outcomes will use linear mixed models and Bonferroni correction.

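### Withdrawing non-compliant mothers and, by implication, replacing them until each arm has 8 evaluable pairs conflicts with the intention-to-treat claim; the analysis set and the allocation of replacements need stating

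*Combined protocol and SAP*

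**What the plan says.** The main Study Design section lists three grounds for withdrawal: "Participants who meet any exclusion criteria during the course of the study, are non-compliant or are lost to follow-up will be withdrawn". It continues: "Provided that there are at least 8 mother/baby pairs with evaluable data in each group, withdrawn participants will not be replaced". The condition applies to each arm separately. What happens below 8 is not written out, but the sentence has little purpose unless replacement then follows.

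The Statistical Plan sets the analysis principle: "All data analyses will employ intention to treat principles". It needs 8 mothers per group at week 4 and covers attrition by over-enrolling: "Assuming a conservative 20% loss to follow-up before week 4, we will enroll enough mother-infant pairs to achieve our desired sample size of 16". No enrolment number is given. If loss is substantial (more than 10% is the example), a linear mixed model is to be fitted.

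On allocation, the Study Design section has the investigational pharmacy randomise mothers after consent, from a schedule prepared with the biostatistician. On compliance, the Growth and Hospitalization section says it is judged from diet records and that no rate will be assessed. The documents do not say how a replacement is allocated, who watches the evaluable count by arm, or whether withdrawn or replaced pairs stay in the analysis.

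**The concern.** Two of the three withdrawal grounds, non-compliance and meeting an exclusion criterion during the study, arise after randomisation. Non-compliance is also closely tied to the primary outcome, because milk DHA depends on what the mother takes. If such mothers are withdrawn, count as non-evaluable and are replaced, the week-4 comparison is no longer between the groups as randomised. It becomes a comparison of mothers who took their supplement and stayed, with each arm refilled to 8, under an intention-to-treat label. Because no compliance rate is assessed and no threshold is given, the decision to withdraw for non-compliance is also discretionary.

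A difference in withdrawal between 200 mg and 1000 mg would itself be a finding. A final 8 versus 8 gives no sign of such a difference if the withdrawn pairs are left out.

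**Working it through.** **1. The plan's own figure.** Inputs from the Statistical Plan: two-fold difference, CV 30%, two-sided level 0.025, power 90%. On the raw scale, with means 1 and 2, the SDs are 0.3 and 0.6, and their root mean square is √((0.09 + 0.36)/2) = 0.474. For 8 per group the noncentrality is 1/(0.474 × √(2/8)) = 4.22 on 14 degrees of freedom. Power is 94.3%, and 8 is the smallest group size that reaches 90%. An unequal-variance test, by simulation, gives 91.9% at 8 and 85.9% at 7. The 8 per group therefore reproduces. (The plan does not state the scale; a log-scale t test would need 6.)

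**2. Enrolment.** Not stated. Derived: 16/(1 − 0.20) = 20, taken as 10 per arm. This is an assumption.

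**3. Chance that an arm falls below 8.** Evaluable is taken to mean at week 4, and losses are taken as independent at 20%.
- P(an arm of 10 keeps at least 8) = 0.3020 + 0.2684 + 0.1074 = 0.6778
- P(at least one arm short) = 1 − 0.6778² = 0.541
- P(exactly one short) = 2 × 0.6778 × 0.3222 = 0.437
- P(both short) = 0.3222² = 0.104
- If exactly 4 of 20 are lost: 1 − C(10,2)²/C(20,4) = 1 − 2025/4845 = 0.582

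**4. Sensitivity.** P(at least one arm below 8), by loss and number enrolled per arm:

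| Loss | 10 per arm | 11 per arm | 12 per arm |
|---|---|---|---|
| 10% | 14% | 4% | 1% |
| 15% | 33% | 13% | 5% |
| 20% | 54% | 30% | 14% |
| 25% | 72% | 49% | 29% |
| 30% | 85% | 68% | 48% |

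With 10 per arm the probability passes one half at a loss of 19.0%. The plan's 20% is for loss to follow-up only. Withdrawals for non-compliance or exclusion criteria come on top and move the trial down the table; the documents give no rate for them.

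**5. Unequal withdrawal.** Suppose 10% loss in one arm and 30% in the other, 10 per arm. The arms fall short with probability 1 − 0.9298 = 0.070 and 1 − 0.3828 = 0.617, and at least one does with probability 1 − 0.9298 × 0.3828 = 0.644. After refilling to 8 and 8, the evaluable counts would show nothing of this difference.

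**6. The two rules side by side.** Intention to treat keeps a mother in her assigned arm whatever she took. The withdrawal rule removes her for not taking it, and the replacement rule puts another in her place. Both can be followed only if withdrawn mothers remain in the analysis, which the documents do not say.

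**The case against.** The replacement sentence is a rule for not replacing. Its converse is implied, and no replacement procedure is written. The plan invokes intention to treat and CONSORT, and provides a mixed model for substantial loss. Nothing excludes withdrawn mothers from the analysis or prevents withdrawals from being reported by arm. This stands to the extent that the plan does not suppress unequal withdrawal: equal counts mask it only if withdrawn pairs are left out and go unreported. It does not remove the conflict. The mixed model can use only data that were collected and kept, and withdrawal for non-compliance is linked to intake, so it is not a harmless form of missing data.

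A reader might infer that replacements are directed to the short arm, so that part of the comparison is not randomised, and that this is more likely than not. The documents do not support that. They have the pharmacy randomise mothers after consent, with no exception for replacements, and a floor of 8 per arm can be met by continuing down the schedule. The 54% is the chance that some arm is short. One arm short and the other not, the case in which steering would arise, has probability 44%. Steering is a risk that the per-arm wording leaves open, not a stated rule.

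It is also fair that 54% is fragile. It rests on an unstated enrolment and on a loss that the plan itself calls conservative.

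Replacing the per-arm floor by a total of 16 might look simpler, but it permits 10 versus 6. If exactly 4 of 20 are lost, that occurs in 2 × C(10,4)/C(20,4) = 420/4845 = 8.7% of cases. With 6 in the higher-mean arm, the variance of the difference rises from (0.09 + 0.36)/8 = 0.05625 to 0.09/10 + 0.36/6 = 0.069, about 23%. The floor is better kept.

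**Conclusion.** The concern holds as an unresolved conflict between the withdrawal and replacement rules and the intention-to-treat claim. Read literally, the plan allows the primary comparison to become one of compliant completers refilled to 8 per arm. The size of the resulting bias cannot be computed, because no rate of non-compliance is given. What can be sized is how often the implied rule would come into play: about 54% of trials with 20 enrolled and independent 20% loss, 30% with 11 per arm, and 14% with 10 per arm and 10% loss. Withdrawals beyond loss to follow-up would raise each figure. Neither non-random allocation of replacements nor concealment of withdrawals is established.

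**What to change.** - State the number to be randomised.
- State that every randomised mother stays in the analysis set under her assigned arm, including those recorded as non-compliant, withdrawn or replaced, and that data collection, above all week-4 milk, continues where possible. Whether she goes on taking the supplement is a separate clinical matter.
- Report withdrawals by arm and reason.
- State that any added mother takes the next concealed entry of the pharmacy's schedule and is never assigned to a named arm, and that only the pharmacy sees counts by arm.
- Keep 8 evaluable pairs per group as the rule for when enrolment stops.

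The cost is a few sentences and an instruction to the pharmacy. An added mother may fall in the arm that is already full, so a few more may be needed. When only one arm is short, with 1:1 entries and 20% loss, each missing pair takes on average 1/(0.5 × 0.8) = 2.5 enrolments, against 1/0.8 = 1.25 if she were directed to that arm. Including non-compliant mothers may slightly dilute the observed difference; that is the price of the intention-to-treat comparison the plan claims.

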- mothers with history of bleeding disorders or taking any other medication that may increase the risk of bleeding
- infants with bleeding disorders or receiving any other medication that may increase the risk of bleeding

Study Procedures:

Maternal Dietary intake and breastmilk samples will be collected and assessed at initiation of supplementation and at weeks 2, 4, and 8. Maternal breast expression and breastfeeding patterns; anthropometry (weight, height, circumferences); exercise patterns; and smoking habits will be obtained at week 4.

Maternal blood and buccal swabs (saliva) will be collected and assessed at baseline and at weeks 4, and 8.

Infant Dietary intake, blood samplesbuccal swabs (saliva), and stool samples will be collected and assessed at baseline and at weeks 2, 4, and 8. – see Figure 3.

Maternal blood collected will be 5 mL at each collection therefore a total of 15 mL whole blood collected for the study. Infant blood collected will be \sim 1 mL at each collection therefore a total of \sim 5 mL whole blood collected. The infant blood will be collected during routine nutritional lab collections which are clustered with standard of care.

The dietary and supplemental intake of the mother will be assessed at The Bionutrition Center using NDSR software and the dietary intake of the infant will be calculated by the Neonatal Dietitian. The fatty acid contents of the breastmilk, blood, and stool samples will be measured by gas chromatography in our laboratory_using Bligh-Dyer extraction (Chloroform: Methanol (2:1))[34]. Cytokine (IL-10, IL 6, IL-8, IL 1B, TNF a, TGF, adiponectin, leptin) and sRAGE concentrations will be examined in maternal milk, and maternal and infant blood samples using a MSD SECTOR® Imager 2400A. This instrument allows for the analyses of 40 individual samples in duplicate at one time using a 96-well format. Infant growth, clinical outcome, and development data will be collected. Breastmilk samples will be analyzed for fatty acids and certain proteins as is routinely analyzed at Human milk banks of North America and clinically at Cincinnati Children's Hospital Medical Center. Cytokine analysis will be performed on infant stool samples. Saliva samples will be analyzed for genetic polymorphisms. Buccal swabs (saliva) will be analyzed for fatty acids.

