An additional teaspoon of fresh milk will be collected at Week 4 and aliquoted into whole, aqueous, and fat layer fractions. Fat layer RNA will be isolated using a MaxwellTM 16 integrated system (Promega, Madison, WI). RNA quantity (target=1000 ng) and quality (A260:A280 target \geq 1.9) will be confirmed prior to RNA sequencing. Na:K ratio, as a marker of mammary gland inflammation, will be assayed on the milk aqueous fraction.

All biological samples will be collected within study time frames as feasible.

Stool will also have bacteria and yeast measured by using 16S ribosomal markers. **Growth and Hospitalization**

Growth measures are standard of care at University NICU and include weekly weight, length, and head circumference measurements and will be extracted from the participant's charts. At discharge we will obtain body composition on the infant using a validated isolette that has non-invasive, volume and mass measurement capability. Cincinnati University Hospital course records that could be pertinent to the study outcomes will be collected from both mother and infant. Compliance will be assessed as part of diet record evaluations; rate of compliance will not be assessed

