Among participants with adequate quality milk fat layer RNA at Week 4, five pairs will be randomly selected from each group for sequencing (matched on gestational week of delivery, milk DHA concentration at baseline, and Week 4 breast milk output level (exceeds, at, or below infant's needs). The remaining will be set aside for future studies. RNA integrity (RIN \geq 7) will be confirmed at the microarray core and then sent to the gene discovery core for RNA-Seq library preparation (Illumina TruSeq RNA kit) and sequencing (Illumina Hi-Seq2500). Libraries will be multiplexed in batches of 10 with at least 30 million 150bp paired-end reads per sample. Sequence reads will be trimmed for quality and then aligned to the human genome using TopHat. We will use Cufflinks to determine gene expression levels, normalized to Fragments Per Kilobase of transcript per Million mapped reads (fpkm). We will identify differentially expressed genes using DESeq and intersect this gene list with known cytokine signaling genes. We will also conduct Gene Set Enrichment Analysis. Significant biomarker genes will be assayed for all participants using TaqManTM qPCR. Power: N=5 pairs per group enables 90% power (α =0.05) to detect 1.5-fold differences between DHA versus placebo for moderate to high abundance genes (FPKM \geq 10) and 3.0-fold differences for low abundance genes (FPKM \sim 1.0).

[name] PhD.,

The University of Cincinnati / Cincinnati Children's Hospital Medical Center, Docosahexaenoic Acid Supplementation to Mothers to Improve Preterm Infant Nutrition and Immune Homeostasis

July 12, 2013

Safety: All records will be kept according to IRB and regulatory standards. All PHI will be stored in a password protected database. All biological sample data will be kept in a separate database from PHI and study identifiers. Written research records, participant contact information, and signed consent forms will be kept in a locked file cabinet near the study coordinator's work station. All data will be entered from source documents into a Redcap database using a password protected, secure server. Individually identifiable information will not be included in the data set or in any reports.

Laboratory samples will be de-identified and stored at Cincinnati Children's Hospital Medical Center and Nationwide Children's in Columbus Ohio.

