Data And Safety Monitoring Plan

Independent review of the ongoing data, patient reports, and adverse events will be reviewed routinely every quarter to determine on going safety. [name], The Medical Director of Clinical research will be our member on the DSMB.

All serious adverse events that are determined to be related to the study intervention and that are unexpected will be reported in an expedited fashion to the FDA, IRB and study DSMB. Serious adverse events that are deemed related will be reported within 7 calendar days of the sponsor's initial receipt of the information. Serious adverse events that are deemed related but not fatal or life-threatening will be reported within 15 calendar days.

On-going Reporting: Serious adverse events not meeting the criteria for expedited reporting and all other adverse events will be reported annually per federal and institutional regulations and guidelines and to the study member of the DSMB per the Data and Safety Monitoring Plan.

Pregnancy and fetal special circumstances will be given through the IRB review. The informed consent is reviewed by the IRB. Quarterly data surveillance for safety will be done by a Neonatologist in the Division of Neonatology and Pulmonary Biology, [name].

Current financial support:

Divisional Funds are the primary source of funding

The PI in the study does receive 8% salary support from a collaboration with:

R01AT006880-01(PI: [name])7/1/2011- 6/30/2015NCCAM/ODSDHA Attenuates Inflammatory Responses through Altering RAGE Signaling

The goal of this grant is to identify the mechanisms associated with decreased inflammation in response to DHA supplementation, specifically through RAGE-mediated signaling. Funding is also provided by **The Division of Neonatology/ Perinatal Research Institute at Cincinnati Children's Hospital, Ohio**. No extra cost outside of standard of practice will be incurred to the patient.

Based on admissions at University Hospital, the anticipated time frame for the study will be 1 year and then a following year for data analysis and manuscript preparation.

0 baseline {within first week of life} *Enroll & Consent Maternal Milk - fatty acids cytokines	2 week Maternal Milk - fatty acids, cytokines, Diet analysis	4 week Maternal - Milk fatty acids, cytokines, , RNA, Na:K ratio	8 week/Discharge Maternal - Milk fatty acids, cytokines, Maternal blood – fatty acids Diet analysis

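### The primary ANOVA of week-4 milk DHA leaves out the baseline milk DHA already collected and names no scale, although the trial is sized on a ratio

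*Combined protocol and SAP*

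**What the plan says.** The primary analysis is one sentence of the Statistical Plan: "ANOVA will be used to compare DHA levels at four weeks in the breast milk of mothers assigned to the different concentrations" of supplement. No covariate, transformation or effect measure is given. The fallback is equally brief: "If we experience substantial loss to follow-up (e.g., > 10% of subjects), we will fit a linear mixed model". It cites a general reference on random-effects models and gives no fixed effects, baseline handling or scale.

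The sample size in the same section is set "to detect a two-fold difference in the DHA levels at four weeks in expressed milk", with a 30% CV, 90% power and two-sided alpha 0.025. That gives 8 mothers per group. The allowance for attrition reads "Assuming a conservative 20% loss to follow-up before week 4".

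Baseline milk is part of the schedule. Study Procedures states "Maternal Dietary intake and breastmilk samples will be collected and assessed at initiation of supplementation and at weeks 2, 4, and 8", and the baseline column of Figure 3 lists "Consent Maternal Milk - fatty acids cytokines". The only analytic use of baseline milk DHA is in the RNA-sequencing paragraph, where the selected pairs are "matched on gestational week of delivery, milk DHA concentration at baseline, and Week 4 breast milk output level". Study Procedures also allows for gaps: "All biological samples will be collected within study time frames as feasible".

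**The concern.** Two choices that affect the primary estimate are left unused or open.

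- **Baseline.** The plan expects baseline milk DHA to be available and thinks it worth balancing in the RNA subset, but the primary comparison ignores it. With 8 mothers per arm, a predictive baseline would narrow the interval at no cost in samples or assays.
- **Scale.** One CV applied to both arms means the raw-scale SD doubles when the mean doubles. A raw-scale ANOVA would pool two unequal SDs and give an absolute difference, whereas the trial is sized on a ratio. The log scale gives equal SDs and a ratio directly.

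At stake are the width of the interval and an effect measure that matches the design. Fixing the scale also removes a choice that could otherwise be made after seeing data from 16 mothers. A ratio alone would not be enough either: the abstract's Study Design aims for 0.8 mol wt% in milk, and a ratio does not show whether that level is reached.

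**Working it through.** **Inputs.** From the Statistical Plan: two-fold difference, CV 30%, two-sided alpha 0.025, power 90%, 8 per group, 20% loss. Assumed, because the documents do not give them: the baseline to week-4 correlation r (range 0 to 0.7), the same 30% CV in both arms, lognormal values, and the missing-baseline patterns.

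**1. Reproducing 8 per group (noncentral t, alpha 0.025).**
- Raw scale, means 1 and 2, SDs 0.3 and 0.6: pooled SD = sqrt((0.3² + 0.6²)/2) = 0.474. Power is 0.899 at n = 7 and 0.943 at n = 8.
- Log scale: SD = sqrt(ln 1.09) = 0.2936, difference ln 2 = 0.693. Power is 0.905 at n = 6, 0.955 at n = 7 and 0.979 at n = 8.
- Enrolment: 16/(1 - 0.2) = 20.

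Eight is the smallest raw-scale n that reaches 90%, which hints at a raw-scale calculation. Eight also satisfies the log-scale requirement, so the intended scale cannot be read off. Power is adequate on either scale.

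**2. Coverage of a nominal 95% interval at a two-fold effect (200,000 lognormal replicates per row).**

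| 200 mg v 1000 mg | Raw, pooled SD | Raw, Welch | Log |
|---|---|---|---|
| 8 v 8 | 0.942 | 0.947 | 0.951 |
| 9 v 9 | 0.942 | 0.947 | 0.949 |
| 10 v 8 | 0.926 | 0.944 | 0.951 |
| 8 v 10 | 0.955 | 0.949 | 0.950 |

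If 20 enrol (10 per arm) and two are lost at random, 10 v 8 and 8 v 10 each have probability 45/190 = 0.237, and 9 v 9 has 100/190 = 0.526. Average raw pooled coverage = 0.237 × 0.926 + 0.237 × 0.955 + 0.526 × 0.942 = 0.941.

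**3. Mean width of the log-scale ANCOVA interval divided by that of the log-scale ANOVA, 8 per arm with week-4 data (60,000 replicates, baselines missing completely at random).**

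| Missing baselines | Handling | r = 0 | r = 0.3 | r = 0.5 | r = 0.7 |
|---|---|---|---|---|---|
| None | – | 1.045 | 0.998 | 0.905 | 0.745 |
| One per arm | pooled-mean imputation | 1.046 | 1.005 | 0.927 | 0.796 |
| One per arm | mothers dropped | 1.143 | 1.090 | 0.990 | 0.817 |
| Two per arm | pooled-mean imputation | 1.046 | 1.011 | 0.948 | 0.843 |
| Two per arm | mothers dropped | 1.276 | 1.216 | 1.104 | 0.912 |

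Break-even is near r = 0.3. With imputation, including lopsided patterns of two missing in one arm and none in the other, coverage is 0.949 to 0.953 and rejection under the null at 0.05 is 0.048 to 0.052.

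**4. Power after the change (simulated, alpha 0.025).** Log-scale ANCOVA gives 96.4%, 97.8%, 99.2% and 99.9% at r = 0, 0.3, 0.5 and 0.7, against 97.9% for log-scale ANOVA.

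**5. Precision of what would be reported, 8 per arm.**
- One arm's geometric mean: 95% CI ×/÷ exp(2.365 × 0.2936/√8) = 1.28. An observed 0.80 mol wt% gives 0.63 to 1.02.
- Unadjusted ratio: 95% CI ×/÷ exp(2.145 × 0.2936 × √(2/8)) = 1.37.

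**The case against.** ANOVA of randomised groups is valid, and with 16 mothers an unadjusted primary analysis is defensible. The gain depends on a correlation that the documents do not give and that may be low: background intake is 23 mg/day against supplements of 200 or 1000 mg, and the baseline sample is taken in the first week of life. Mean width also hides variation between trials. The ANCOVA interval is wider than the ANOVA interval in about 81% of simulated trials at r = 0, 58% at r = 0.3 and 28% at r = 0.5. Matching the RNA pairs on baseline shows that the value is expected to be available, not that it predicts week 4. The coverage loss is small and arises only if the raw scale is used, which is an inference. The mixed model could treat baseline as a repeated outcome, which would keep mothers without a baseline sample and need no imputation; the text does not exclude this. The switch to it is not certain, because the 10% trigger is an example and the 20% loss is called conservative.

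All of this stands, and it limits the point to an improvement. It does not remove it: the worst case is an interval about 5% wider, the scale is unstated in both analyses, and a mixed model that might handle baseline well has not been specified to do so. One further question is also open: the sizing uses alpha 0.025, while the 0.05 stated for DHA concentrations follows the infant-blood text. The level for the milk comparison should be settled, but the proposed model does not depend on it.

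**Conclusion.** The point holds as a cheap improvement, with medium confidence. The stated test and its power are sound. Adding baseline on the log scale costs about 5% in interval width if baseline is uninformative, breaks even near r = 0.3, and saves about 9% at r = 0.5 and 25% at r = 0.7. Naming the log scale is worthwhile at any correlation: it matches the ratio and CV used for sizing, and its interval covers 95% where a raw-scale pooled interval would average 94%, or 93% at 10 v 8. These figures rest on lognormal data, a 30% CV in both arms, 8 per arm for the width comparisons, and assumed correlations.

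**What to change.** In the Statistical Plan:

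- Define the primary analysis as log week-4 milk DHA regressed on arm, with log baseline milk DHA as covariate.
- Keep mothers who lack a baseline sample by imputing the log-baseline mean pooled over both arms.
- Give the mixed-model fallback the same scale and covariate, with post-baseline visits as outcomes and the week-4 contrast as the estimate.
- Report the 1000 mg to 200 mg geometric mean ratio with its 95% CI.
- Report each arm's week-4 level with 95% CI on the original scale, beside the 0.8 mol wt% target.
- If an absolute difference is also wanted, give it with a Welch interval.

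The cost is SAP wording and one degree of freedom; there are no new samples, assays or participants. With pooled-mean imputation the worst case stays at about 5% wider even with two baselines missing per arm. Dropping those mothers would raise it to 28%.
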